5.0 STUDY DESIGN

5.1 Overview of Study Design

In the proposed CTN multi-site effectiveness trial, a diverse set of drug-using participants entering treatment at collaborating CTPs will be randomly assigned to receive 12 weeks of: (1) TAU or (2) a modified version of TAU which includes access to the computerized TES psychosocial intervention and incentives for abstinence from drugs of abuse and completion of TES modules. We will evaluate the effectiveness of including this computerized intervention as part of TAU to determine if patient use of TES enhances patient outcomes.

Due to the comprehensive, science-based, psychosocial treatment offered by TES, and based on prior work with TES and motivational incentives (Bickel, Marsch et al., 2008) and other work with motivational incentives (e.g., CTN trial published by Petry et al., 2005a), we hypothesize that the modified TAU+TES intervention will promote significantly greater drug abstinence and treatment retention relative to TAU.

5.2 Duration of Study and Visit Schedule

All participants will be asked to participate in a 12-week trial in which they attend the treatment study site at least twice weekly (for a total of 24 visits across the trial period). A 12-week period was selected to best reflect the typical treatment episode duration for the target population in outpatient CTPs. Additionally, detailed participant tracking procedures (see Section 9.5) will be employed to locate participants during the trial and particularly at week 12 and at 2 postintervention follow-up time points (3- and 6-months post-intervention). All participants (in both study conditions) will be asked to provide urine samples and breath alcohol tests at each twice weekly visit (as described in the Section 7.2.1 Assessments below). Participants in the TAU condition will be asked to participate in individual/group therapeutic sessions in accordance with the standard frequency of counseling at their CTP (as noted in Section 6.5 below, collaborating CTPs will offer TAU at least twice weekly), while those in the modified TAU+TES condition will be asked to participate in twice weekly TES sessions and less frequent therapy sessions/group counseling sessions at the treatment site (design details provided in Section 9.4 below). Participants will also be asked to complete scheduled assessments at these visits as needed, in accordance with the assessment timeline (as described in Section 7 Assessments). Participants who are absent on the day of a scheduled urine sample collection can provide a sample the next time they attend the CTP. Participants may be permitted to attend the CTP on a previously unscheduled day in order to provide urine samples and complete assessments. Urine samples must be provided on non-consecutive days within a week for a sample to qualify for incentive procedures (for those who are in the condition that receive incentives) and for contribution to the primary abstinence outcome.

6.0 STUDY POPULATION

6.1 Inclusion Criteria

- Male and female patients (≥ 18 years) accepted for outpatient, substance abuse treatment at a participating CTP study site.
- Self-report any substance use problem, including alcohol as long as they also report other substance use in addition to alcohol.
- (1) Report use of a drug of abuse within 30 days prior to screening or (2) have exited a controlled environment (e.g., detoxification unit, hospital, or correctional facility) within 30 days of screening and report use of a drug of abuse within 60 days prior to screening. This sample was selected to ensure a CTP-friendly and real-world oriented effectiveness trial.
- Participants must be within the first month of initiating treatment at a collaborating CTP to ensure that scheduled psychosocial interventions can be initiated early on in treatment for all participants.
- Self-report a planned substance abuse treatment episode of at least 3 months (the planned evaluation phase in this trial).

Note that because few community clinics use formal diagnostic procedures in practice, individuals will not be required to meet DSM-IV criteria for abuse or dependence to participate in this study (although this will be assessed at baseline). Participants can also have had any number of prior substance abuse and/or psychiatric treatment episodes prior to their current substance abuse treatment episode.

All participants will provide written, informed consent, approved by local institutional review boards. A wide range of contact information will be obtained at baseline in order to locate subjects and achieve maximum adherence and follow-up rates (as described in detail in Section 9.5 below).

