6.5 CTP Characteristics and Rationale

CTPs participating in this trial will:

- (a) Offer outpatient, community-based treatment for individuals with a wide variety of substance use disorders. As Treatment as Usual (TAU) differs in Opioid Treatment Programs relative to other outpatient CTPs, Opioid Treatment Programs will not serve as study sites in this trial.
- (b) Require participants in TAU to participate in at least 2-therapeutic sessions onsite per week, approximately 2 hours (group and/or individual sessions) for a minimum of 12 weeks. Note that CTPs that require fewer sessions will be excluded to prevent asking participants in this trial to attend the treatment site more often solely for the purposes of participating in this trial (as this would not then reflect TAU and would

likely negatively impact participant retention). Additionally, CTPs that offer only intensive outpatient treatment (e.g., daily attendance requirements) will be excluded, as (1) intensive outpatient treatment, when provided, is typically provided only at initial stages of treatment, and (2) intensive outpatient treatment as a treatment modality is being offered with decreasing frequency in light of recent trends within managed care systems to reduce the number of treatment sessions for which reimbursement is provided. Programs that offer intensive outpatient treatment but then provide stepped-down care into less intensive outpatient treatment will not be excluded.

- (c) Project an average treatment intake rate of at least 1 eligible study client per week.
- (d) Project a minimum of approximately 40 study clients to be enrolled at the site within 1 year.
- (e) Provide adequate space to accommodate research assistants and study protocol procedures including on-site urinalysis collection and testing and space for computers for participants' access of TES and for site monitoring.
- (f) Willing to allow participants in the modified TAU+TES condition to reduce their frequency of participation in group and/or individual counseling sessions (and to participate in twice weekly TES sessions).
- (g) Willing to require all therapists at their CTP to follow study procedures with patients participating in this trial.

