9.0 STUDY PROCEDURES

9.1 Informed Consent Procedures

Informed consent procedures must be conducted within 30 days of the date that participants entered the CTP for a new treatment episode. Every effort will be made to conduct consent procedures as soon as possible after a patient enters a CTP for a new treatment episode; however, a 30-day window allows for a broader array of eligible patients to be considered for study participation. As part of the informed consent procedure, the schedule for earning incentives for drug negative urines and alcohol breath tests and for completion of TES modules will be presented to and discussed with the participant.

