9.4.3 Subject and Treatment Discontinuation Criteria/Stopping Rules

Participants will be considered to be active in the study throughout the 12 week period following their baseline assessment, independent of the frequency with which they attend the CTP. If a participant is terminated or discharged from the CTP, then they are no longer eligible to participate in the active treatment portion of this study. A standardized criterion for CTP discharge will be adopted during the conduct of this trial (e.g., no contact with a patient for 30 consecutive days). Participants will still be tracked and asked to complete all assessments, including treatment week 12, 3- and 6-month follow up assessment visits.

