14.2.2 Primary Retention Measure

The second primary outcome measure will be time to drop-out from treatment (including TAU) and will be treated as time-to-event data (time until last face to face contact). Drop-out is considered an event, and for each participant who does not complete all 12 weeks of treatment, time (in weeks) from start of treatment to drop-out from treatment is recorded, with values potentially ranging from 0 through 11. Participants completing all 12 weeks of treatment will have time value recorded as 12 weeks and will be considered censored at that time.

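### The planned 3-month treatment episode is not anchored to randomisation, so a patient who finishes care on schedule can be scored as a retention drop-out

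*Protocol*

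**What the plan says.** - **Entry window.** Section 6.1: "Participants must be within the first month of initiating treatment at a collaborating CTP". Section 9.1: "Informed consent procedures must be conducted within 30 days of the date that participants entered the CTP for a new treatment episode". Section 6.3 also counts the month from the intake date of a new episode. Up to 30 days of an episode may therefore have passed at entry.
- **Planned length.** Section 6.1: "Self-report a planned substance abuse treatment episode of at least 3 months (the planned evaluation phase in this trial"). No starting point is given.
- **Study clock.** Section 9.4.3: "Participants will be considered to be active in the study throughout the 12 week period following their baseline assessment".
- **Discharge.** The same section has this rule for people who leave the program: "terminated or discharged from the CTP, then they are no longer eligible to participate in the active treatment portion of this study". It makes no exception for planned completion. It adds that these participants are still followed and asked for all assessments.
- **Retention event.** Section 14.2.2: "Drop-out is considered an event, and for each participant who does not complete all 12 weeks of treatment", a time to drop-out is recorded. Only those who complete 12 weeks are censored, and section 14.4.2 repeats this.
- **A statement the criteria do not back up.** Section 9.5.1 says in passing that eligibility presupposes being able to come in person for 12 weeks of treatment. No item in 6.1 or 6.2 secures 12 further weeks of planned care after randomisation.

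**The concern.** A patient can meet every listed criterion and still have less than 12 weeks of planned treatment ahead. When that care ends on schedule, sections 9.4.3 and 14.2.2 together remove the patient from active treatment and record a drop-out. Retention is a co-primary outcome, and planned completion is the opposite of what it is meant to capture. These events occur at dates set by the calendar in both arms and carry no information about treatment, so they blur the contrast and lower the reported 12-week retention.

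Abstinence is tested only in half-weeks 17-24 (section 14.4.1). A planned discharge in weeks 9-12 may end access to the computerised intervention during the period in which it is judged.

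**Working it through.** **Plan's own figure.** Section 14.4.2 assumes 12-week retention of 35% (TAU) and 50% (TAU+TES), N = 500 and two-sided alpha 0.025.
- Hazard ratio = ln 0.35 / ln 0.50 = 1.515.
- Expected events = 250 × 0.65 + 250 × 0.50 = 287.5.
- Power = Φ(√287.5 / 2 × ln 1.515 − 2.241) = Φ(1.28) = 89.9%. The stated 90% is reproduced.

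**Care left at entry.** Days left = planned length − days already in treatment, compared with the 84 days the study needs. Take 3 months as 91 days.
- Entry on day 30: 91 − 30 = 61 days = 8.7 weeks. The test window opens after day 56, so planned care ends 5 days into it and 23 of its 28 days fall after planned discharge.
- A shortfall arises whenever 91 − d < 84, that is, for entry later than day 7.
- With entry day uniform on the whole days 0-30 (assumed), 23/31 = 74% of patients at the floor have under 12 weeks left. The mean shortfall over all floor patients is (1 + 2 + … + 23)/31 = 8.9 days.
- No shortfall is possible if the planned length is at least 84 + 30 = 114 days (16.3 weeks).

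**Effect on retention power.** Log-rank power was simulated under these assumptions: 250 per arm; constant drop-out hazards giving 35% and 50% at 12 weeks; entry day uniform on 0-30; a given share of patients with a 91-day episode and the rest with long ones. The ranges cover repeated runs of 3,000 to 10,000 trials per cell.

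| Share at the floor | Recorded 12-week retention, TAU / TAU+TES (planned completion = event) | Power, planned completion = event | Power, planned completion = censored |
|---|---|---|---|
| 0% | 35% / 50% | about 90% | about 90% |
| 10% | 32% / 46% | 87-88% | 88-90% |
| 25% | 28% / 41% | 83-84% | 88-90% |
| 50% | 22% / 31% | 76-78% | 88-90% |
| 100% | 9% / 13% | 63-67% | 86-90% |

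The 100% row is an extreme bound. Censoring recovers nearly all of the loss, because it gives up only some late follow-up and adds no uninformative events.

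**The case against.** **Intent.** The parenthesis in 6.1 equates the 3 months with the trial's evaluation phase, section 9.5.1 speaks of 12 weeks of attendance, and the relocation exclusion in 6.2 looks forward from entry. This stands: 12 study weeks were evidently meant. It makes the correction uncontroversial, but the operative criterion still does not say so.

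**Size.** The protocol's 3 months is a floor, and 9.1 asks for consent as early as possible, so few patients may be affected. The 35% and 50% rates may also already include planned leavers, in which case the calculation double-counts them. Both points stand, and the power loss can only be given as a range.

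**SAP.** Coding of discharge reasons is often left to the SAP. That is fair for detail, but eligibility, the consequence of discharge and the event definition are fixed in the protocol, and a SAP cannot restore treatment time lost through eligibility.

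**Stronger readings that the documents do not support.**
- A reader might note that 5.2 says "A 12-week period was selected to best reflect the typical treatment episode duration for the target population in outpatient CTPs" and that sites in 6.5 need only require "group and/or individual sessions) for a minimum of 12 weeks", and so take 84 days as the episode. That leaves 84 − 30 = 54 days and puts exit before the test window. But an 84-day plan falls short of 3 calendar months read literally, section 5.2 explains the trial's length, and section 6.5 sets a site attendance requirement. None of these gives the planned episode of an enrolled patient.
- A reader might infer that weeks 9-12 abstinence data are lost. Section 9.4.3 keeps discharged participants in all assessments, section 9.5 allows them off site, and the analysis is by intention to treat. Access to the intervention may end; data loss is possible but not automatic.
- A reader might think the retention clock could start at CTP intake. Sections 8.1 and 9.4.3 effectively tie it to the 12 weeks after baseline.

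**Conclusion.** The point holds as a fault of wording with a real but unquantified effect. Followed literally, the protocol can admit patients with as little as about 8.7 weeks of planned care left and then score their scheduled completion as drop-out. The consequence is dilution of the retention comparison, with planned ends expected at the same calendar dates in both arms. It is not a bias in favour of either arm.

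On a 91-day episode and uniform entry over 0-30 days, the stated 90% power falls to about 87% if 10% of patients are at the floor and about 84% if 25% are. At 50% it is about 77%, and at the 100% extreme about 65%. There is no loss if everyone plans about 16 weeks or more. Because the share at the floor and the spread of entry days are not given, the severity is moderate. The documents do not support calling the primary analyses invalid.

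**What to change.** 1. **Section 6.1:** require at least 12 weeks of planned CTP treatment remaining at randomisation, in line with 9.5.1.
2. **Section 14.2.2 (and 14.4.2):** record the discharge reason and do not count planned completion as a drop-out event. Censor it at that date, with a sensitivity analysis that treats the patient as retained to week 12.
3. **Section 9.4.3:** reconcile the consequence of discharge with the 12-week intervention for participants whose CTP episode ends as planned.

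The cost is some wording, one screening question and one data field. The downside is that a few patients with short planned episodes become ineligible. The eligibility change has to come before enrolment, because lost treatment time cannot be recovered in the analysis.

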6.2 Exclusion Criteria

- Individuals will be excluded if they are participants in Opioid Treatment Programs (OTPs) and/or receiving opioid replacement medication, as TAU differs considerably in OTPs relative to other outpatient programs. If participants in CTPs are receiving some non-opioid pharmacotherapy for their substance use disorder or psychiatric disorder, we will systematically track this and consider these medication data in planned analyses as appropriate.
- Individuals will be excluded if they plan to move out of the area within the next 3 months.
- Individuals will be excluded if they have insufficient ability to provide informed consent to participate.
- Individuals will be excluded if they lack sufficient ability to use English to participate in the consent process, the interventions or assessments.

Ability to provide informed consent and English proficiency will both be confirmed through the informed consent process and the completion of a comprehension quiz. Participants will be asked to answer a number of questions related to study procedures outlined in the consent form. Any questions that the participant answers incorrectly will form the basis of discussion with a staff person. After discussion, the staff person will make a final determination of English

comprehension and ability to provide informed consent. Further, 100% of the informed consent documentation is monitored according to the quality assurance plan.

6.3 Subject Recruitment

Potential participants will be informed about the opportunity to participate in this trial at the time they enter treatment at a collaborating CTP or within the first 30 days of treatment at the CTP. A variety of strategies may be employed to ensure that all new intakes are informed about the opportunity to participate in the trial. For example, CTP intake workers may introduce the patient to a study Research Assistant so they can learn about the opportunity to participate in the study or arrange a follow-up time to do so. Alternatively, all new intakes can be provided with a form, providing a brief description of the trial, which they can sign to indicate they would like to learn more about the trial. They can provide their contact information on this form and a Research Assistant will then contact them (assuming the patient and Research Assistant are unable to speak at the patient's time of intake). Note that by completing this form, patients are not consenting to participate in the trial but are giving permission for research staff to contact them both while they are at the CTP and/or via phone to inform them about more details of the study. Additionally, IRB-approved study flyers and posters may be posted at collaborating CTPs with information about how to contact research staff to learn more about the opportunity to participate in the study. Staff at the CTPs will also be informed about the study so that they can answer questions and consult with potential participants that are interested in the study.

During the initial contact between potential participants and research staff, staff will conduct a brief screen to assess if participants meet eligibility criteria for the study and do not meet exclusionary criteria for the study. Only information necessary to assess individuals' eligibility will be obtained at this initial screening (described in Sections 6.1 & 6.2 above). If a participant is eligible and interested in joining the study, s/he can complete Informed Consent procedures (described in Section 9.1.) with the Research staff at this initial visit (or within one month of their intake date for a new treatment episode at the CTP).

Based on prior CTN trials targeting a similar population (Petry et al., 2005), we expect that approximately 55% of participants will be female and about 50% of participants will be minorities.

6.4 Number of CTP Sites

We plan to sample approximately 10 outpatient CTPs from the CTN platform and recruit approximately 50 participants per site (see justification of sample size in Section 14.4). Sites will be selected for the geographic, ethnic, racial, and gender diversity they offer, as well as their prior history of successful CTN collaborations and ability to demonstrate a sufficient flow of study participants.

6.5 CTP Characteristics and Rationale

CTPs participating in this trial will:

- (a) Offer outpatient, community-based treatment for individuals with a wide variety of substance use disorders. As Treatment as Usual (TAU) differs in Opioid Treatment Programs relative to other outpatient CTPs, Opioid Treatment Programs will not serve as study sites in this trial.
- (b) Require participants in TAU to participate in at least 2-therapeutic sessions onsite per week, approximately 2 hours (group and/or individual sessions) for a minimum of 12 weeks. Note that CTPs that require fewer sessions will be excluded to prevent asking participants in this trial to attend the treatment site more often solely for the purposes of participating in this trial (as this would not then reflect TAU and would

likely negatively impact participant retention). Additionally, CTPs that offer only intensive outpatient treatment (e.g., daily attendance requirements) will be excluded, as (1) intensive outpatient treatment, when provided, is typically provided only at initial stages of treatment, and (2) intensive outpatient treatment as a treatment modality is being offered with decreasing frequency in light of recent trends within managed care systems to reduce the number of treatment sessions for which reimbursement is provided. Programs that offer intensive outpatient treatment but then provide stepped-down care into less intensive outpatient treatment will not be excluded.

- (c) Project an average treatment intake rate of at least 1 eligible study client per week.
- (d) Project a minimum of approximately 40 study clients to be enrolled at the site within 1 year.
- (e) Provide adequate space to accommodate research assistants and study protocol procedures including on-site urinalysis collection and testing and space for computers for participants' access of TES and for site monitoring.
- (f) Willing to allow participants in the modified TAU+TES condition to reduce their frequency of participation in group and/or individual counseling sessions (and to participate in twice weekly TES sessions).
- (g) Willing to require all therapists at their CTP to follow study procedures with patients participating in this trial.
- (h) Able to provide records of all participants' attendance in individual and group counseling sessions. Note that tracking forms for systematically documenting this information will be provided to each CTP so that these data can be summarized and provided in study reports when describing the type and amount of TAU study participants received.
- (i) Not routinely offer (as part of TAU) contingency management interventions to their patients in which they provide prizes or other tangible incentives to participants contingent on evidence of drug abstinence.

